## 9.1 Efficacy variables based on seizures

In general, efficacy variables based on seizures will be measured using data obtained from EP0034 subject diaries.

Each seizure code in the clinical database will be mapped to exactly 1 of the ILAE seizure codes based on the 1981 ILAE classification (Seizure Count eCRF module).

### 9.1.1 Percentage of seizure-free days

The percentage of seizure-free days (as defined in [Section 3.2.20](#)) will be summarized by seizure time intervals (as defined in [Section 3.2.21](#)) and also for the entire Treatment Period. This will also be grouped by enrollment group. This will be repeated, separately by seizure type (simple partial, complex partial, or partial, secondary generalized).

### 9.1.2 Seizure frequency per 28 days

The following analyses will only be done for subjects who participated in SP0969.

Seizure frequency per 28 days (as defined in [Section 3.2.13](#)) will be summarized descriptively and presented graphically.

### 9.1.3 $\geq 50\%$ reduction in 28-days partial-onset seizure frequency

The following analyses will only be done for subjects who participated in SP0969.

The number and percentage of subjects with  $\geq 50\%$  reduction in 28-day partial-onset seizure frequency ( $\geq 50\%$  responders as defined in [Section 3.2.15](#)) will be summarized by seizure time intervals (as defined in [Section 3.2.21](#)) and also for the entire Treatment Period. This will be repeated, separately by seizure type (simple partial, complex partial, or partial, secondary generalized). Any subject with seizure data during the time interval will be included in the summary for that seizure time interval and by seizure type.

### 9.1.4 $\geq 75\%$ reduction in 28-days partial-onset seizure frequency

The analyses described in [Section 9.1.3](#) for percentage of subjects with  $\geq 50\%$  reduction in 28-days partial-onset seizure frequency will also be performed for study subjects with  $\geq 75\%$  reduction in 28-day partial-onset seizure frequency ( $\geq 75\%$  responders) for subjects who participated in SP0969.

### 9.1.5 Absolute and percent reduction in total partial-onset seizures

The following analyses will only be done for subjects who participated in SP0969.

Absolute and percent reduction from Baseline (as defined in [Section 3.2.14](#)) in total partial-onset seizures will be summarized by seizure time intervals (as defined in [Section 3.2.21](#)) and also for the entire Treatment Period. This will be repeated, separately by seizure type (simple partial, complex partial, or partial, secondary generalized).

### 9.1.6 Seizure-free status

The number and percentage of subjects who achieved seizure-free status (as defined in [Section 3.2.18](#)) will be summarized for the entire Treatment Period. This will be presented by completer cohorts (as defined in [Section 3.2.19](#)) and repeated by enrollment groups.

The number and percentage of study subjects seizure-free among completer cohorts (as defined in Section 3.2.19) will also be presented separately by seizure type (simple partial, complex partial, or partial, secondary generalized).

Seizure-free status will also be presented by seizure time intervals (as defined in Section 3.2.21) and repeated by enrollment groups. The number and percentage of study subjects with seizure-free status at the end of each time interval during the treatment period will be presented separately by seizure type (simple partial, complex partial, partial, secondary generalized).

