### 3.2.17 Seizure-free day

A seizure-free day is defined as a day where no seizures were reported in the seizure diary and seizures were assessed. Days in the seizure diary which are marked as “not done” on the eCRF will not be counted as a seizure-free day.

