### 3.2.18 Seizure-free status

Subjects will be considered seizure-free for a given period if the subject completes the period, reports zero seizures during the period, and has no more than 10% of days in the period for which seizure data is not available (ie, “not done” is noted on the Seizure Frequency eCRF module). Seizure diary days where “not done” has been reported for days when subjects were participating in a previous study will not be counted toward the 10% of days with missing seizure diary data (eg, missing seizure data due to a previous study will not count against a subject in the assessment of seizure-free status). If a subject enrolls in a short-term iv substudy, days of participation in the substudy will also not be considered in the assessment of seizure-free status.

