### 3.2.19 Completer cohorts

A completer cohort will be defined as the subset of subjects in the Full Analysis Set (FAS) that were enrolled and treated with LCM for a specified duration of time. For example, a 6-month completer cohort consists of subjects enrolled and treated with LCM for at least 6 months where a month is defined as 28 days.

Subjects will be classified as belonging to one of the following completer cohorts for the purpose of subgroup analyses:

- 6 months
- 12 months
- 18 months
- 24 months

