### **3.5.2 Full Analysis Set**

The Full Analysis Set (FAS) will be used for the analysis of seizure data and will consist of all subjects in the SS, who have at least 1 completed post-Baseline seizure diary. Subjects whose efficacy data could not be source verified will be excluded from the FAS.

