#### **4.6 Use of an efficacy subset of subjects**

The FAS, defined in [Section 3.5.2](#), is the primary analysis set for efficacy analyses. No additional efficacy subsets are defined for this study.

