### **9 EFFICACY ANALYSES**

The study efficacy variables include seizure counts (assessed using seizure diaries in order to evaluate preliminary evidence of efficacy during long-term exposure in this population), the Clinical Global Impression of Change, the Caregiver Global Impression of Change, and quality of life assessments (PedsQL and health care resource use).

All study efficacy variables will be summarized for the FAS, overall and repeated by enrollment group (where applicable), using the levels defined in [Section 3.2.12](#). All summaries of efficacy data are descriptive; no statistical testing will be performed.

All efficacy variables will be listed.

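### By-type seizure freedom and by-type seizure-free days count children who never had the seizure type as free of it

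*SAP*

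**What the plan says.** SAP 9.1.6 has two by-type presentations of seizure freedom. One gives "The number and percentage of study subjects seizure-free among completer cohorts" for each of the three partial-onset types. The other reports subjects "with seizure-free status at the end of each time interval during the treatment period will be presented separately by seizure type". SAP 9.1.1 does the same for the percentage of seizure-free days.

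The definitions that feed these tables are:

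- **Seizure-free status (SAP 3.2.18):** "Subjects will be considered seizure-free for a given period if the subject completes the period, reports zero seizures during the period", with at most 10% of diary days missing.
- **Completer cohort (SAP 3.2.19):** FAS subjects "that were enrolled and treated with LCM for a specified duration of time".
- **FAS (SAP 3.5.2):** it "will consist of all subjects in the SS, who have at least 1 completed post-Baseline seizure diary", less those whose efficacy data could not be source verified.
- **Other efficacy subsets (SAP 4.6):** "No additional efficacy subsets are defined for this study".
- **Seizure-free day (SAP 3.2.17):** "a day where no seizures were reported in the seizure diary and seizures were assessed".

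Protocol 4.2.3 and SAP 2.2.3.3 list seizure freedom, total and per type, among the variables computed for every subject in the study. SAP 6.3.1 summarizes each subject's history of seizure types but does not connect it to 9.1.1 or 9.1.6.

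**The concern.** A subject enters with partial-onset seizures, and under SAP 6.3.1 any one of the three types is enough to qualify. Many subjects may therefore lack at least one type. If they stay in the by-type denominators, they enter the numerator almost automatically, because they have nothing to become free of.

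A reader will take a by-type seizure-free percentage to describe children who have that type. As planned, the figure mixes their outcome with the prevalence of the type in the cohort. A rare type would look well controlled and a common type poorly controlled, even if the outcome among affected children were identical. By-type seizure freedom is a listed other efficacy variable, so these figures can be expected in the report.

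**Working it through.** **1. Tracing the denominator.** 9.1.6 names the completer cohort. The cohort depends on FAS membership and duration of treatment, and the FAS depends on dosing, a diary and source verification. The status rule depends on completion, zero seizures and diary completeness. Seizure type appears in none of these. The general sentence in SAP 3.1, that denominators should suit the purpose of the analysis, sets no seizure-type rule.

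**2. Tracing the numerator.** 3.2.17, 3.2.18 and 3.2.20 are written for seizures in general. If zero seizures meant zero of any type, the three by-type tables on one cohort would print the same number. The variable is also defined per seizure type. The workable reading is therefore zero seizures of that type, and a child without the type meets it.

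**3. A consequence that needs no assumption.** Anyone with no seizures at all has none of each type. With one common cohort as denominator, every by-type rate is at least the overall rate.

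**4. Size for seizure freedom.** The plan states no figure to reproduce and gives no by-type inputs, so everything here is assumed:

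- p = share of subjects with the type: 20%, 50%, 80%
- f = share of those classed as free of it: 10%
- Among subjects without the type:
  - c = share completing the period: 100% in completer cohorts, 70% to 100% in interval tables
  - q = share meeting the diary condition: 70% to 100%
  - o = new onset of the type: 0% to 10%

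Reported rate = p·f + (1 − p)·c·q·(1 − o).

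The low end uses q = 0.7 and o = 0.1, with c = 0.7 for interval tables. The high end uses c = q = 1 and o = 0. At p = 0.5 in a completer cohort, the low end is 0.05 + 0.5 × 0.7 × 0.9 = 0.365 and the high end is 0.05 + 0.5 = 0.550.

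| p | Rate among those with the type | Completer cohorts | Interval tables |
|---|---|---|---|
| 20% | 10% | 52% to 82% | 37% to 82% |
| 50% | 10% | 37% to 55% | 27% to 55% |
| 80% | 10% | 21% to 28% | 17% to 28% |

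At p = 0.5 in completer cohorts, the share of those counted as free who never had the type is 0.315/0.365 = 86% at the low end and 0.5/0.55 = 91% at the high end. With p = 0.5 and c = 1, changing f to 5% gives 34% to 53%, and f = 20% gives 42% to 60%.

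**5. Size for seizure-free days.** A subject without the type and without new onset has 100% seizure-free days for it. The median is therefore 100%, whatever happens in affected children, when (1 − p)(1 − o) > 0.5. That means p below 50% at o = 0, or below 1 − 0.5/0.9 = 44% at o = 10%. For the mean with o = 0 and an assumed 70% among those with the type, the table would show 0.2 × 100 + 0.8 × 70 = 76% at p = 80%, and 0.8 × 100 + 0.2 × 70 = 94% at p = 20%.

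**6. Related by-type tables.** Percent change (SAP 3.2.14) divides by Baseline frequency, so it is undefined when the by-type Baseline is 0. SAP 3.1 and 4.2.1 point towards leaving such subjects out, while 9.1.3 says anyone with seizure data in the interval is included, also by type. The rule needs writing down.

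**The case against.** The strongest reply is that the SAP leaves a rule unwritten and does not state a wrong one. No by-type version of seizure freedom is given, and the sentence in 3.1 would let a programmer restrict the denominator. One could also show overall seizure freedom within subgroups of children who have each type. The three tables would then differ and no inflation would arise. It is true that 3.1 permits a restriction. It does not require one, and 9.1.6 names the completer cohort. The subgroup reading does not fit a variable defined as no seizure per seizure type.

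A second reply is that the protocol itself assigns the variable to every subject, and that the share of all subjects with no seizure of a type is a coherent quantity. This stands: for seizure freedom the SAP follows its protocol, and the problem is one of interpretation. By-type seizure-free days, however, are a SAP addition, since Protocol 4.2.2 lists only the overall measure.

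Third, the impact is limited and the numbers are illustrative. Both are true. There is no hypothesis testing, efficacy is not the primary objective, and a wide range of assumed inputs shows direction and possible scale only. Type history will be summarized for the Safety Set, so some context exists, but not beside the percentages it would qualify.

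**Conclusion.** The concern holds. Followed as written, the by-type parts of 9.1.6 and 9.1.1 count a child who never had a seizure type as a success for that type, subject only to the completion and diary conditions for seizure freedom. The direction of the distortion follows from the definitions. Its size depends on how many children lack each type, which the documents do not give. Under the assumed inputs, a 10% rate among affected children would be reported as anything from 17% to 82%. The planned and restricted figures would agree if every subject had the type.

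The damage is confined to descriptive by-type tables. Total partial-onset seizure freedom, the secondary variable (overall percentage of seizure-free days) and the safety results are untouched. It should be fixed because the by-type figures will be misread and the remedy uses data already collected.

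**What to change.** In the by-type parts of 9.1.6 and 9.1.1:

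- Define freedom as zero seizures of that type. Use as denominator the subjects with that type in the ILAE Seizure Classification History (SAP 6.3.1), for both enrollment groups.
- Print the number with the type beside each percentage.
- Report new onset separately, among subjects without the type.
- Record the departure from the protocol's population in SAP 3.9.
- Add a sensitivity denominator of recently active types, because lifetime history keeps inactive ones. For SP0969 this is at least one seizure of the type in the 8-week Baseline diary (SAP 3.3). For both groups it could be a count above zero in the Historical Seizure Counts module (SAP 6.3.3, 4 weeks before Baseline), if that module was completed in both studies.

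As secondary clarifications, state in 9.1.3 to 9.1.5 that by-type percent change and responder tables use SP0969 subjects with a by-type Baseline frequency above zero, and give the number excluded. In 3.2.14, either reverse the sign of the absolute reduction to Baseline minus treatment or call it a change. That last point is clerical and alters no responder classification.

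The cost is SAP wording, one flag per seizure type and one new-onset row per table. The by-type tables will have smaller n, and the main ones will keep some inflation from inactive types. The sensitivity denominator shows how much.

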## 9.2 Analysis of other efficacy variables

The following other efficacy variables will be computed for all subjects in this study and summarized for the FAS.

### 9.2.1 Clinical Global Impression of Change

The Clinical Global Impression of Change is a 7-point categorical rating scale in which the investigator should provide his/her assessment of the subject's clinical status, compared to Baseline, including an evaluation of seizure frequency and intensity, the occurrence of AEs, and subject's functional status. This will be assessed at least once per year and will be completed according to the tabular schedule of study procedures.

The number and percentage of subjects by Clinical Global Impression of Change value will be summarized by visit and Last Visit. This will be repeated by enrollment group. The denominator for the percentage calculation will be based on the number of subjects with non-missing values. In addition, the 3 improvement values (Very much improved, Much improved, and Minimally improved) grouped as "Improved" and the 3 worsening values (Minimally worse, Much worse, and Very much worse) grouped as "Worsened", together with the "No change" group will be summarized by visit and Last Visit. The denominator for the percentage calculation will be based on the number of subjects with non-missing values.

Clinical Global Impression of Change data will be listed.

### 9.2.2 Caregiver's Global Impression of Change

The Caregiver's Global Impression of Change is a 7-point categorical rating scale in which the caregiver (including parent/legal guardian) should provide his/her assessment of the subject's clinical status, compared to Baseline, including an evaluation of seizure frequency and intensity, the occurrence of AEs, and subject's functional status. This will be assessed at least once per year and will be completed according to the tabular schedule of study procedures.

The number and percentage of subjects by Caregiver's Global Impression of Change value will be summarized by visit and Last Visit. This will be repeated by enrollment group. The denominator for the percentage calculation will be based on the number of subjects with non-missing values. In addition, the 3 improvement values (Very much improved, Much improved, and Minimally improved) grouped as "Improved" and the 3 worsening values (Minimally worse, Much worse, and Very much worse) grouped as "Worsened", together with the "No change" group will be summarized by visit and Last Visit. The denominator for the percentage calculation will be based on the number of subjects with non-missing values.

Caregiver's Global Impression of Change data will be listed.

### **9.2.3 Pediatric Quality of Life Inventory (PedsQL)**

The PedsQL is a validated instrument that consists of generic core scales suitable for use with pediatric populations, including those with acute or chronic health conditions. The PedsQL will be completed up to two times per year and will be assessed according to the tabular schedule of study procedures. The Section 3.2.22 details how the scores for the core domains are calculated.

#### **9.2.3.1 Pediatric Quality of Life Inventory Ages for $\leq 24$ Months**

The multidimensional PedsQL  $\leq 24$  months generic core scales encompass the following core domains for pediatric HRQoL measurement: Physical Functioning, Physical Symptoms, Emotional Functioning, Social Functioning, and Cognitive Functioning.

Calculated values and changes from Baseline for the total scale score (all items), the psychosocial health summary score, the physical health summary score and each of the 5 scale scores will be summarized for each visit and for Last Visit. This will be repeated by enrollment group. All changes from Baseline will only be calculated for visits when the subject uses the same form of the questionnaire as administered at baseline.

All PedsQL  $\leq 24$  months data will be listed.

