- PedsQL assessment (form consistent with age at the visit; however, the form used in the primary study must be used for at least 1 year after the Baseline assessment of the primary study, as described in Section 9.3)
- Contact IXRS
- Review LCM return and compliance
- Dispense LCM (the investigator may adjust the LCM dose according to Table 7-1)
- Reminder to complete subject diary on a daily basis
- Review withdrawal criteria
- Adverse event reporting
- Health care resource use

A telephone contact will be made approximately 4 weeks after Visit 9 (end of Week 56, Section 8.1.2). Subjects will be scheduled to return to the clinic for the next visit in approximately 8 weeks.

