9.3 PedsQL

The PedsQL is a validated instrument that consists of generic core scales suitable for use with pediatric populations, including those with acute or chronic health conditions (Varni et al, 2001). The PedsQL will be administered according to the tabular schedules of study procedures (Section 5.2). The PedsQL will only be administered in countries where a validated translated version is available.

The PedsQL measurement model consists of developmentally appropriate forms for pediatric subjects 1 month to 12 months, 13 months to 24 months, 2 years to 4 years, 5 years to 7 years, 8 years to 12 years, and 13 years to 18 years of age. Self-report is measured for pediatric subjects ≥ 5 years to ≤ 18 years of age, and parent proxy report of child health-related quality of life (HRQoL) is measured for pediatric subjects ≤ 4 years of age. The PedsQL appropriate for each subject's age should be completed, with the following exception: If a subject ages up to the next form of the PedsQL within 1 year after the Baseline assessment of the primary study, the form that was used at the Baseline assessment should be completed for 1 year after the Baseline assessment, and subsequently the form consistent with his/her age at the time of assessment should be completed.

The multidimensional PedsQL generic core scales encompass the essential core domains for pediatric HRQoL measurement: Physical Functioning, Emotional Functioning, Social Functioning, and School Functioning. The PedsQL assessment is retrospective to the prior 4 weeks, and individual items are scored using a 5-point Likert scale (never, almost never, sometimes, often, or always). A total health summary score ranging between 0 and 100 is calculated from the sum of the raw scores, with higher scores indicating higher HRQoL.

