### 3.2.6 Last Visit

The Last Visit for all assessments in EP0034 is the last non-missing assessment during the Treatment Period. All scheduled and unscheduled assessments within this time period will be considered. Last Visit will be determined separately for each study procedure where Last Visit is mentioned within this document.

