### **3.2.22 Pediatric Quality of Life Inventory (PedsQL)**

The PedsQL is a validated instrument that consists of generic core scales suitable for use with pediatric populations, including those with acute or chronic health conditions. Self-report is measured for pediatric subjects  $\geq 5$  years to  $\leq 18$  years of age, and parent proxy report of child health-related quality of life (HRQoL) is measured for pediatric subjects  $\geq 1$  month to  $\leq 4$  years of age. The PedsQL Measurement Model consists of developmentally appropriate forms for pediatric study subjects  $\geq 1$  month to  $\leq 12$  months,  $\geq 13$  months to  $\leq 24$  months,  $> 2$  years to  $\leq 4$  years,  $\geq 5$  years to  $\leq 7$  years,  $\geq 8$  years to  $\leq 12$  years, and  $\geq 13$  years to  $\leq 18$  years of age. For each subject, the same version that is used at Baseline should be used for 12 months and thereafter the age appropriate age versions should be used.

For versions intended for subjects  $\leq 24$  months of age, PedsQL infant scale scores will be calculated for each of the following 5 PedsQL scales:

- Physical Functioning

- Physical Symptoms
- Emotional Functioning
- Social Functioning
- Cognitive Functioning

For versions intended for subjects >2 years of age, PedsQL generic core scale scores will be calculated for each of the following 4 PedsQL scales:

- Physical Functioning
- Emotional Functioning
- Social Functioning
- School Functioning

For versions intended for subjects >8 years of age, Physical Functioning refers to questions “About my health and activities”; Emotional Functioning refers to questions “About my feelings”; Social Functioning refers to questions “How I get along with others”; School Functioning refers to questions “About school”.

The PedsQL assessment is retrospective to the prior one month, and individual items are scored using a 5-point Likert scale (0 to 4 representing responses of: never, almost never, sometimes, often, or almost always). These scores of 0 to 4 will be transformed by the following formula in order to generate scores of 0, 25, 50, 75, and 100 where a higher value represents a better health-related quality of life (HRQoL):

$$\text{Item transformed score} = 100 - (\text{item raw score} \times 25)$$

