#### **9.2.3.2 Pediatric Quality of Life Inventory Ages $> 2$ years**

The multidimensional PedsQL  $> 2$  years generic core scales encompass the following core domains for pediatric HRQoL measurement: Physical Functioning, Emotional Functioning, Social Functioning, and School Functioning.

Calculated values and changes from Baseline for the total scale score (all items), the psychosocial health summary score, the physical health summary score and each of the 4 scale scores will be summarized for each visit and for Last Visit. This will be repeated by enrollment group. For subjects 5 years and older at Baseline, changes from Baseline will be calculated for all visits, even when the questionnaire version used is different from the one at Baseline. For subjects less than 5 years at baseline, the change from Baseline will be calculated only when the same questionnaire version is used at Baseline and post-Baseline. All PedsQL  $> 2$  years data will be listed.

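### Infant PedsQL change from Baseline cannot exist once the form switches at 1 year, so the Last Visit change leaves out many or all infants assessed to Week 96

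*SAP*

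**What the plan says.** Protocol 9.3 lists "developmentally appropriate forms for pediatric subjects 1 month to 12 months, 13 months to 24 months, 2 years to 4 years", followed by three older forms. A child who outgrows a form is not moved at once: "the form that was used at the Baseline assessment should be completed for 1 year after the Baseline assessment", and after that the form goes by current age. SAP 3.2.22 says the same: "the same version that is used at Baseline should be used for 12 months and thereafter the age appropriate age versions should be used".

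PedsQL is scheduled at Visit 1 and Weeks 20, 52, 72 and 96, and at early termination. Protocol 8.1.10 and 8.1.12 ask for the age-appropriate form at Weeks 72 and 96, with no exception.

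For the forms up to 24 months, SAP 9.2.3.1 summarises values and changes at each visit and at Last Visit, subject to "All changes from Baseline will only be calculated for visits when the subject uses the same form of the questionnaire as administered at baseline". SAP 9.2.3.2 applies the same limit to children under 5 years at Baseline: "the change from Baseline will be calculated only when the same questionnaire version is used at Baseline and post-Baseline". For children aged 5 or older at Baseline, change is computed at all visits whichever form is used.

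SAP 3.2.6 states: "The Last Visit for all assessments in EP0034 is the last non-missing assessment during the Treatment Period". It is determined once per study procedure. The SAP does not say whether the infant forms and the older forms count as one procedure or several.

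**The concern.** The form-switch rule, the same-form rule and the Last Visit definition are each reasonable alone. Together they may leave the infant Last Visit change without the children who stayed longest. A child followed to Week 96 has a last PedsQL on a form that the same-form rule disallows, while a child who stopped in the first months has a last PedsQL that it allows.

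A reader would take a row labelled change at Last Visit as quality of life at the end of exposure, which is what the study's other objectives ask about. The observed-value and change rows under that label would also describe different children.

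**Working it through.** The documents give no figure to reproduce. The check follows a child's age and form through the schedule.

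**Inputs.** Form bands and the 1-year hold: Protocol 9.3, SAP 3.2.22. SAP band edges (≥1 to ≤12 months, >12 to ≤24 months): SAP 3.1. Visit window of ±7 days: Protocol 8. Visit 1 is the primary study's final Transition Visit: Protocol 8.1.1. Let P be the weeks from primary-study Baseline to Visit 1. P is not given for SP0967, so it is assumed and varied from 1 to 40 weeks.

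**Step 1: does every infant-form child switch?** With Baseline age a in months:
- 1–12 month form: a + 12 ≥ 13, outside the band.
- 13–24 month form: a + 12 ≥ 25 in completed months, or > 24 with the SAP edges, outside the band.

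On a 0.05-month age grid, the number still in the Baseline band after 12 months is 0 of 480 (completed months) and 0 of 461 (SAP edges).

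**Step 2: which visits fall after the switch?** Days since primary Baseline = 7P + 7 × week ± 7.
- Week 96: at least 672 − 7 = 665 days, past 365 for any P.
- Week 72: at least 504 − 7 = 497 days, past 365 for any P.
- Week 52: at least 7P + 357 days, past 365 once 7P > 8 days. From P = 2 weeks it is always past; at P = 1 week it can fall either side.
- Week 20: at most 7P + 147 days, within 365 while P ≤ 218/7 = 31.1 weeks. At the early end of the window (133 days) the limit is 232/7 = 33.1 weeks.

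Week 20 is therefore the last scheduled visit with an infant change for P up to about 31 weeks. For P of about 34 weeks or more, only Visit 1 remains. One qualification concerns Week 52. SAP 3.2.3 assigns an early-termination assessment to the next visit at which that assessment is due. A child who leaves after Week 20 but within the year would therefore be reported under Week 52. Any infant change in that column would come from such children.

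**Step 3: Last Visit with PedsQL as one procedure.** A child assessed at Week 96 has that record as Last Visit, on a different form, so no change is computed. Grid ages contributing: 0 of 480 and 0 of 461. The contributors are children whose last PedsQL fell within about 1 year of Baseline.

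**Step 4: Last Visit within infant-form records only.** Take children assessed at all visits.
- Began on the 13–24 month form: no later infant record exists, so 100% contribute Week 20 (P = 8 to 30 weeks).
- Began on the 1–12 month form: the child contributes only if already past the 13–24 month band at Week 52. Otherwise the last infant record is on the 13–24 month form, again a mismatch. The condition is a + (7P + 364)/30.4375 ≥ 25 (completed months) or > 24 (SAP edges).
 - P = 8, completed months: 420/30.4375 = 13.80, so a ≥ 11.20; share (13 − 11.20)/12 = 15%.
 - P = 30, SAP edges: 574/30.4375 = 18.86, so a > 5.14; share (12 − 5.14)/11 = 62%.

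So 15–62% contribute and 38–85% do not. These shares assume ages spread evenly across the band.

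**Step 5: the 2–4 year form.** Week 96 is 672/365.25 = 1.84 years after Visit 1. A child under 5 at Baseline who enters EP0034 older than about 5 − 1.84 = 3.16 years is 5 or more at Week 96 and past the hold. On the Step 3 reading that child has no Last Visit change under SAP 9.2.3.2.

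**The case against.** The same-form rule is deliberate and sound: SAP 3.2.22 scores five scales on the infant forms and four on the older ones. Observed values are still summarised, the data are listed and n is always shown, so empty cells at Weeks 72 and 96 would be visible. SAP 9.2.3.1 treats the infant forms in their own section, and deriving Last Visit inside that section would let many completers contribute Week 20. PedsQL change is one of the other efficacy variables in a descriptive study. All of this stands and limits the weight of the point. It does not settle which record supplies the Last Visit change, and the reading that favours the SAP is not stated and still loses many of the youngest children.

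A reader might infer more than the documents support:
- *Only early leavers contribute.* A child who stays but has no PedsQL after Week 20 (a missed visit, or no validated translation of the next form) also contributes. An early leaver assessed after the switch does not.
- *No completer ever contributes.* That holds only with PedsQL as one procedure (Step 3 against Step 4).
- *CBCL and BRIEF have the same fault.* Their versions are summarised as separate questionnaires, and only children who cross an age limit change version.
- *The Week 52 instruction contradicts Protocol 9.3.* Protocol 8.1.8 says "the form used in the primary study must be used for at least 1 year after the Baseline assessment of the primary study", but it refers to 9.3 for the rule, and the Table 5-2 footnote agrees with 9.3.
- *The row selects on outcome.* Nothing in the documents links leaving early to quality of life.

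**Conclusion.** The point holds in a limited form. Infant PedsQL change from Baseline is empty by construction at Weeks 72 and 96. No Week 52 visit can supply it if P is about 2 weeks or more. That is plausible, since Visit 1 closes the primary study's Transition Period, but it remains an assumption for SP0967.

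On the literal Last Visit definition, children assessed at Week 96 are dropped from the infant change. The row then rests mainly on children who left within about a year of Baseline or have no later PedsQL. On the narrower reading, the loss falls on those who began on the 1–12 month form. Children under 5 on the 2–4 year form are affected when they switch before their last assessment. The summary is selective or ambiguous, depending on how it is programmed, and should be settled in the SAP.

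**What to change.** Change the SAP only. In 3.2.6, 9.2.3.1 and 9.2.3.2, wherever the same-form rule applies to PedsQL change, define Last Visit as the latest available Treatment Period assessment on the Baseline form. Report n and the timing of that assessment (typically Week 20). For visits after the switch, present observed values only.

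The cost is a few sentences and one derived flag, with no new data. There are two limits. The infant Last Visit change will mostly describe about Week 20 and not the end of exposure, which a footnote should say. Some children will still not contribute: Table 5-1 lets the Visit 1 PedsQL be replaced by the one from the primary study's final Maintenance Visit, so a child who missed Week 20 may have no same-form record in the Treatment Period.
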